5.3.2.2. Adverse events

Incomplete AE-related dates will be imputed as follows:

- If the AE onset date is missing completely, then the onset date will be replaced by the start of study treatment.
- If only the day part of the AE onset date is missing, but the month and year are equal to the start of study treatment, then the AE onset date will be replaced by the start of study treatment. For example, if the AE onset date is --/JAN/2015, and study treatment start date is 15/JAN/2015, then the imputed AE onset date will be 15/JAN/2015.
- If both the day and month of the AE onset date are missing but the onset year is equal to the start of study treatment, then the onset date will be replaced by the start of study treatment. For example, if AE onset date is --/---/2014, and study treatment start date is 19/NOV/2014, then the imputed AE onset date will be 19/NOV/2014.
- In all other cases the missing onset day or missing onset month will be replaced by 1.
- Incomplete stop date will be replaced by the last day of the month (if day is missing only), if not resulting in a date later than the date of patient's death. In the latter case the date of death will be used to impute the incomplete stop date.
- In all other cases the incomplete stop date will not be imputed. If stop date of AE is after the date of cut-off, outcome of AE is ongoing at cut-off.

5.3.2.3. Prior and concomitant medications

Incomplete prior/concomitant medication dates will be imputed as follows:

- If the medication date is missing completely, then the medication date will be replaced by the start of study treatment.
- If the day of medication date is missing, but the month and year are equal to the start of study treatment, then the medication date will be replaced by the start of study treatment. For example, if the medication start date is --/JAN/2015, and study treatment start date is 15/JAN/2015, then the imputed medication start date will be 15/JAN/2015.
- If both the day and month of medication start date are missing but the start year is equal to the start of study treatment, then the medication date will be replaced by the start of study treatment. For example, if the medication start date is --/---/2014, and study

treatment start date is 19/NOV/2014, then the imputed medication start date will be 19/NOV/2014.

- In all other cases the missing medication day or missing medication month will be replaced by 1.
- Incomplete stop date will be replaced by the last day of the month (if day is missing only), if not resulting in a date later than the date of patient's death. In the latter case the date of death will be used to impute the incomplete stop date.
- In all other cases the incomplete medication stop date will not be imputed.

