5.9. Concomitant Treatments

Medications or vaccinations specifically prohibited in the [Exclusion Criteria](#) are also not allowed during the active treatment period, except for administration of inactivated vaccines.

If there is a clinical indication for one of these or other medications or vaccinations specifically prohibited during the trial, discontinuation from study therapy or medication/vaccination may be required. The final decision on any supportive therapy or

vaccination rests with the investigator and/or the patient's primary physician. However, the decision to continue the patient on study therapy or medication/vaccination schedule requires the mutual agreement of the investigator, the sponsor, and the patient.

Concomitant treatment considered necessary for the patient's well-being may be given at the discretion of the treating physician.

Concomitant medications, blood products, non-drug interventions, and treatments, including herbal supplements, will be recorded from 28 days prior to the start of study treatment and up to 90 days after the last dose of study treatment (Arm A) or 90 days after the End of Treatment (EOT) visit (Arm B).

All concomitant medications will be recorded in the CRF including supportive care drugs (eg, antiemetic treatment and prophylaxis) and the drugs used to treat adverse events or chronic diseases, and non-drug supportive interventions (eg, transfusions). During study treatment, concomitant medications should be reviewed at each study visit, and any prohibited treatments should be discussed and appropriately managed.

Given that recording of non-serious AEs ends when a patient begins a new anti-cancer therapy ([Section 8.2](#)), recording of concomitant medications associated with these non-serious AEs should also end. However, given that SAEs must continue to be recorded up to 90 days after the last dose of study treatment(s) even if the patient begins a new anti-cancer therapy, concomitant medications associated with these SAEs must also be recorded.

As per Protocol Amendment 6, following the final OS update, concomitant medications/treatments will not be captured in the CRF unless they contribute to or are associated with the treatment for an AE.

Concurrent anticancer therapy with agents is not allowed, other than avelumab in patients randomized to Arm A. Medications intended solely for supportive care (ie, antiemetics, analgesics, megestrol acetate for anorexia) are allowed.

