6.5.2.2. Protocol deviations

All protocol violations that impact the safety of the patients and/or the conduct of the study and/or its evaluation will be reported. These include:

- Patients who are dosed on the study despite not satisfying the inclusion criteria
- Patients who develop withdrawal criteria whilst on the study but are not withdrawn
- Patients who receive the wrong treatment or an incorrect dose
- Patients who receive an excluded concomitant medication
- Deviations from GCP.

The identification of these and other CSR-reportable deviations will be based on the inclusion/exclusion criteria or other criteria presented in the protocol.

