6.5.4. Concomitant medications and non-drug treatments

The following analyses will be based on the safety analysis set by treatment arm.

Concomitant medications are medications, other than study drugs, which started prior to first dose date of study treatment and continued during the on-treatment period as well as those started during the on-treatment period. **Prior medications** are medications, other than study drugs and pre-medications for study drug, which are started before the first dose of study treatment.

Prior and concomitant medications will be summarized from the ‘General Concomitant Medications’ eCRF page. Pre-medications for study drug will also be summarized separately from the ‘Pre-Medication Treatment’ eCRF page.

Summary of prior medications, summary of concomitant medications and summary of pre-medications will include the number and percentage of patients by Anatomical Therapeutic Chemical (ATC) Classification level 2 and preferred term. A patient will be counted only once within a given drug class and within a given drug name, even if he/she received the same medication at different times. If any prior or concomitant medication is classified into multiple ATC classes, the medication will be summarized separately under each of these ATC classes. The summary tables will be sorted on decreasing frequency of drug class and decreasing frequency of drug name in a given drug class. In case of equal frequency regarding drug class (respectively drug name), alphabetical order will be used. In case any specific medication does not have ATC classification level 2 coded term, it will be summarized under ‘Unavailable ATC classification’ category.

A listing of prior medications and a listing of concomitant medications will be created with the relevant information collected on the ‘General Concomitant Medications’ eCRF page. A listing of pre-medications will be created with the relevant information collected on the ‘Pre-Medication Treatment’ eCRF page.

All concurrent procedures, which were undertaken any time during the on-treatment period, will be listed according to the eCRF page ‘General Non-drug Treatments’.

A listing of concurrent procedures will be created with the relevant information collected on the ‘General Non-drug Treatments’ eCRF page.

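### Some missing medication start dates are set to the start of study treatment without checking the stop date, so a drug known to have stopped earlier is tabulated as concomitant and not as prior

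*SAP*

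**What the plan says.** SAP 5.3.2.3 moves an incomplete medication start date to the start of study treatment in three cases:

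- Nothing is known: "If the medication date is missing completely, then the medication date will be replaced by the start of study treatment".
- The month matches: "If the day of medication date is missing, but the month and year are equal to the start of study treatment".
- Only the year is known and it matches: "If both the day and month of medication start date are missing but the start year is equal to the start of study treatment".

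For other partial starts, "In all other cases the missing medication day or missing medication month will be replaced by 1".

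Stop dates have separate bullets. A stop lacking only its day goes to month-end, limited by the date of death. Any other incomplete stop is left as it is. Neither stop-date bullet refers back to the start date.

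SAP 6.5.4 then classifies the records. A prior medication is one begun before first dose. A concomitant medication is one begun earlier that carried on into the on-treatment period, "as well as those started during the on-treatment period". That last limb has no stop-date condition. Under SAP 3.5.1 and 5.2.7 the on-treatment period opens on the day of first dose in Arm A and on Cycle 1 Day 1 in Arm B.

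Protocol 5.9 says that concomitant medications and treatments "will be recorded from 28 days prior to the start of study treatment".

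**The concern.** The collection window reaches back before treatment, so drugs that ended before first dose belong in the data. For such a drug the stop date alone settles the classification: it is prior and cannot be concomitant, however poorly its start was recorded. The rule ignores that information and can place the start after the stop.

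At stake are the two medication summaries, which would show too much concomitant use and too little prior use, and the listings, which would print impossible date sequences. SAP 5.3.1 requires imputed values to be shown and flagged in listings. The flag tells a reader that a date was imputed, but it does not correct the tables.

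**Working it through.** The plan states no figure to reproduce, so the check is a trace of the rules on sample records.

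**Inputs.** The treatment start dates and partial start dates are those in the SAP's own examples in 5.3.2.3 (15/JAN/2015 with start --/JAN/2015; 19/NOV/2014 with start --/---/2014), plus one completely missing start. The stop dates are assumed, and each lies within 28 days before treatment.

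**Reading of the rule.** The medication date in the first bullet is taken to be the start date, because the later examples use start dates and stop dates have their own bullets.

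**Step 1: apply 5.3.2.3.** Imputed start = start of study treatment in all three cases. Gap = imputed start − recorded stop.

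| Case | Treatment start | Recorded start | Recorded stop | Imputed start | Gap |
|---|---|---|---|---|---|
| 1 | 15/JAN/2015 | missing | 05/JAN/2015 | 15/JAN/2015 | 15 − 5 = 10 days |
| 2 | 15/JAN/2015 | --/JAN/2015 | 10/JAN/2015 | 15/JAN/2015 | 15 − 10 = 5 days |
| 3 | 19/NOV/2014 | --/---/2014 | 31/OCT/2014 | 19/NOV/2014 | 19 days |

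**Step 2: apply 6.5.4.** Each imputed start falls on the first day of the on-treatment period, so each drug is concomitant. None starts before first dose, so none is prior. The stop dates show that both results are wrong.

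**Step 3: look for an override.** There is none in SAP 5.3.1, 5.3.2.3 or 6.5.4. SAP 5.3.3.4 shows the opposite practice: the imputed start of a new anti-cancer therapy is capped by that therapy's end date.

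**Step 4: bound the start.** Set imputed start = min(start of study treatment, stop date). The starts become 05/JAN/2015, 10/JAN/2015 and 31/OCT/2014. All three precede first dose and none of the drugs continues into treatment, so all three are prior only.

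**Step 5: find the limits of the effect.**

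- Partial starts in another month or year go to day or month 1 and are not moved to treatment start.
- If the stop is unknown, or falls on or after treatment start, counting the drug as concomitant is an ordinary cautious choice.
- A stop lacking only its day, in the month of first dose, goes to month-end. It stays concomitant under the bounded rule too, which is reasonable because the timing is then uncertain.
- SAP 6.5.4 counts a patient once per drug class and once per drug name. A misplaced record therefore changes a count only if that patient has no other qualifying record for the same class or drug.
- The efficacy endpoints do not use these dates. The last-contact derivation (SAP 5.3.3.1) does not list medication dates, and new anti-cancer therapy has its own eCRF pages and its own rule.
- The immune-related adverse event algorithm (SAP Appendix 1, step 4) links medications by adverse event identifier, not by imputed date.

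**The case against.** The strongest defence is that the rule follows the SAP's own safety convention: the adverse event rule in 5.3.2.2 also moves incomplete onsets to treatment start with no stop-date check, and counting doubtful drugs as concomitant is cautious. This stands where timing is unknown. It fails where a stop date before treatment is known, because nothing is then in doubt. The parallel is also imperfect. Protocol 8.2 has adverse events recorded on the CRF only from first dose or Cycle 1 Day 1, so treatment start is a natural floor for them. Medications are collected from earlier.

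It can also be said that 5.3.3.4 is stricter because its date drives censoring and the end of the on-treatment period. That explains the extra care there, but it is no reason to contradict recorded dates here.

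Three stronger readings are tempting, and the documents do not support them.

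- **False protocol deviations.** SAP 6.5.2.2 lists "Patients who receive an excluded concomitant medication" among reportable deviations, so a reader might infer that a drug properly stopped before first dose would be reported as one. But that section identifies deviations from the eligibility criteria and other protocol criteria. It cites neither the imputed dates nor the 6.5.4 classes. A systemic steroid would also be a poor illustration. Protocol 5.1 requires treatment within 3 days after randomization, so a stop on 10 January with first dose on 15 January means randomization on 12 to 15 January, 2 to 5 days after the stop. Protocol 4.2, exclusion criterion 14, restricts immunosuppressives in the 7 days before randomization. Such use is either an eligibility deviation whatever is imputed, or exempt.
- **Distorted durations.** The record's implied duration is negative, but SAP 6.5.4 plans no analysis of medication duration.
- **A frequent problem.** A 28-day look-back does not show how many records end before treatment, or how many of those lack a usable start date.

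**Conclusion.** The rule is wrong as written for a narrow, definable set of records: a start date that is completely missing, or partial and matching the month or year treatment began, together with a stop date (recorded or imputed to month-end) before treatment. A year-only stop in an earlier year belongs to the same set when the start is completely missing. Every record in the set receives the wrong class.

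The number of such records cannot be determined from the documents, and no percentage is offered. The consequence is confined to the descriptive prior and concomitant medication tables and listings, in both arms. This is a minor correction. It is worth making because the rule overrides recorded data and the remedy is simple. The conclusion assumes that the program follows 5.3.2.3 and 6.5.4 literally, with no unwritten check on date order.

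**What to change.** Add one sentence to SAP 5.3.2.3: when the stop date, recorded or imputed to month-end, is earlier than the start of study treatment, the imputed start is the earlier of the date the existing rule gives and the stop date. For a stop known only by year, where that year is before the year treatment began, the imputed start is no later than 31 December of the stop year. State that such records count as prior only. This matters for year-only stops, which 5.3.2.3 leaves unimputed and a program might otherwise treat as continuing.

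The cost is that sentence and one programming condition. No new data are needed and no endpoint analysis changes.

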5.3.2.4. Exposure

No imputation will be done for first dose date. Date of last dose of study drug, if unknown or partially unknown, will be imputed as follows:

- If the last date of study drug is completely missing and there is no End of Treatment eCRF page and no death date, the patient should be considered to be ongoing and use the cut-off date for the analysis as the last dosing date
- If the last date of study drug is completely or partially missing and there is EITHER an End of Treatment eCRF page OR a death date available (within the cut-off date), then imputed last dose date is:
 - = 31DECYYYY, if only Year is available and Year < Year of min (EOT date, death date)
 - = Last day of the month, if both Year and Month are available and Year = Year of min (EOT date, death date) and Month < the month of min (EOT date, death date)
 - = min (EOT date, death date), for all other cases.

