3.4. Baseline Variables

3.4.1. Study drug, study treatment and baseline definitions

In this study, ‘study drug’ refers to avelumab or BSC and ‘study treatment’ (or ‘treatment arm’) refers to one of the following:

- Arm A = Avelumab + BSC;
- Arm B = BSC alone.

Start and end dates of study treatment:

- For Arm A:
 - The date/time of first dose of study treatment is the earliest date/time of non-zero dosing of the study drug.
 - The date/time of last dose of study treatment is the latest date/time of non-zero dosing of the study drug.

- For Arm B:
 - The date of start of study treatment is defined as the date of Cycle 1 Day 1 (C1D1); a patient is considered to be treated in Arm B if they complete the C1D1 visit.
 - ‘End date of BSC’ (last dose of study treatment) is the date of completion or discontinuation as collected in the ‘Disposition - Treatment Phase’ eCRF page.

Definition of baseline:

Definition of baseline for efficacy and PRO analyses

The last measurement prior to randomization will serve as the baseline measurement for efficacy and PRO analyses. If such a value is missing (since per protocol the first PRO assessment is planned to occur on Cycle 1 Day 1), the last measurement prior to the first dose of study treatment will be used as the baseline measurement except for analyses of tumor assessments data where the baseline assessment would be considered as missing.

Definition of baseline for immunogenicity analyses (Arm A only)

The last available assessment prior to the start of treatment with avelumab is defined as ‘baseline’ result or ‘baseline’ assessment. If an assessment is planned to be performed prior to the first dose of avelumab in the protocol and the assessment is performed on the same day as the first dose of avelumab, it will be assumed that it was performed prior to avelumab administration, if assessment time point is not collected or is missing.

Definition of baseline for safety analyses

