5.2.7. Definition of on-treatment period

Safety endpoints will be summarized based on the on-treatment period unless otherwise specified. On-treatment period is defined as follows:

- Arm A: time from the first dose of study treatment through minimum (30 days + last dose of study treatment, start day of new anti-cancer drug therapy – 1 day);
- Arm B: time from Cycle 1 Day 1 through minimum (30 days + end date of BSC, start day of new anti-cancer drug therapy – 1 day).

Here, 'end date of BSC' is the date of completion or discontinuation as collected in the 'Disposition - Treatment Phase' eCRF page.

Safety data collected outside the on-treatment period as described above will be listed and flagged in listings but will not be summarized.

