      YYYY = Year of min [max(PD date + 1, last dose of study treatment + 1), end
      date of new anti-cancer therapy], AND
      MMM = Month of min [max(PD date + 1 day, last dose of study treatment + 1
      day), end date of new anti-cancer therapy]
    THEN
      imputed start date = min [max(PD date + 1 day, last dose of study treatment + 1
      day), end date of new anti-cancer therapy];
    ELSE IF
      YYYY = Year of min [max(PD date + 1, last dose of study treatment + 1), end
      date of new anti-cancer therapy], AND
      MMM > Month of min [max(PD date + 1 day, last dose of study treatment + 1
      day), end date of new anti-cancer therapy]
    THEN
      imputed start date = 01 MMM YYYY;
    ELSE IF
      YYYY < Year of min [max(PD date + 1, last dose of study treatment + 1), end
      date of new anti-cancer therapy]
    THEN
      imputed start date = DAY (Last day of MMM) MMM YYYY;
    ELSE IF
      YYYY > Year of min [max(PD date + 1, last dose of study treatment + 1), end
      date of new anti-cancer therapy]
    THEN
      imputed start date = 01 MMM YYYY.
```

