6.5.3.1. Exposure to avelumab

The dose level for avelumab is calculated as actual dose administered/weight (mg/kg). The last available weight of the patient on or prior to the day of dosing will be used.

For Cycle X, actual cycle start date for each patient is

- the start date of dosing in the Cycle X day 1 visit eCRF exposure page, if the patient received avelumab on that visit (ie, avelumab with dose>0 at that visit)

- the first day of assessments in the Cycle X day 1 visit, if the patient did not receive avelumab on that visit (ie, dose=0 for avelumab at that visit). Use start date in the exposure page if available; if start date is not available then use date of collection of vital signs on Cycle X day 1 visit.

Actual cycle end date for each patient is,

- for all cycles X except the last cycle, actual cycle end date = actual cycle (X+1) start date – 1 day;
- for the last cycle, actual cycle end date = actual cycle start date + 28 – 1 day

Cycle duration (weeks) = (actual cycle end date – actual cycle start date + 1)/7

Intended duration of treatment with avelumab (weeks) =

(end date – date of first dose of avelumab + 1)/7,

where end date = start date of last cycle with non-zero dose of avelumab + 28 – 1

Duration of exposure to avelumab (weeks) =

(last dose date of avelumab – first dose date of avelumab + 14)/7

Cumulative dose is the sum of the actual doses of avelumab received.

Actual Dose Intensity (DI)

- Overall actual DI (mg/kg/4-week cycle) = [overall cumulative dose (mg/kg)] / [intended duration of treatment with avelumab (weeks)/4].

Relative Dose Intensity (RDI)

- Intended DI (mg/kg/4-week cycle) = [intended cumulative dose per cycle] / [intended number of 4-weeks in a cycle] = [20 (mg/kg)] / [1 (4-week cycle)] = 20 (mg/kg/4-week cycle)
- Overall RDI (%) = $100 \times [\text{overall actual DI}] / [\text{intended DI}]$
= $100 \times [\text{overall actual DI}] / [20 \text{ (mg/kg/4-week cycle)}]$

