9. APPENDICES

Appendix 1. Immune-Related Adverse Events

The MedDRA PTs and clusters for irAEs are defined in the Safety Review Plan (SRP) for avelumab.

Immune-related AEs (irAEs) will be programmatically identified as outlined in Table 16. This case definition is hierarchical, ie, each step is only checked for patients and events that have already met the prior step.

Table 16. Case Definition for irAEs

Step	Selection Criteria	Additional Notes
1	Event selected based on a list of pre-specified MedDRA PTs within clusters. These are included in the SRP as Tier1 events (Immune-mediated xxxx). If AE matches the list, then it is in for the next step	
2	AE onset during 1 st study drug administration or anytime thereafter through 90 days after last dose of study treatment.	This is regardless of start of new anti-cancer drug therapy and regardless of TEAE classifications
3	Answer in the AEECRF page to 'Was another treatment given because of the occurrence of the event' is 'YES'	
4	AE treated with corticosteroids or other immunosuppressant therapy. For endocrinopathies only: AE required hormone replacement	Look in the conmed pages for AE identifiers that match the AEs from Step 3. For each of such AEs if A) OR B) OR C) below are met then the AE is in for the next step A) conmed ATC code is in (H02A, H02B, D07, A01AC, S01BA, S01BB, L04AA, L04AB, L04AC, L04AD, L04AX, A07EA) and AEPT is in any of the irAE clusters. B) conmed ATC code is in (H03A, H03B) and AEPT is in one of the irAE clusters associated with "Immune-mediated endocrinopathies" C) conmed ATC code is A10A and AEPT is in the irAE cluster associated with "Immune-mediated endocrinopathies: Type I Diabetes Mellitus"

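### The last-dose imputation in SAP 5.3.2.4 has no branch for a known month in an earlier year than EOT or death, so it assigns a last dose that contradicts the recorded month

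*SAP*

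**What the plan says.** SAP 5.3.2.4 (Exposure) covers a last study-drug date that is wholly or partly missing when an EOT page or a death date is available. Call the earlier of those two dates the reference date. There are three outcomes:

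1. Only the year is known and it precedes the reference year: "31DECYYYY, if only Year is available and Year < Year of min (EOT date, death date").
2. Year and month are both known: "Last day of the month, if both Year and Month are available and Year = Year of min (EOT date, death date"), with the further condition that the month is earlier than the reference month.
3. Otherwise: "min (EOT date, death date), for all other cases".

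SAP 3.4.1 sets the Arm A definition that the imputation stands in for: "The date/time of last dose of study treatment is the latest date/time of non-zero dosing of the study drug". For Arm B, the end of BSC is taken from the treatment-phase disposition page.

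The last dose date is then used in several places:

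- Exposure duration in weeks (SAP 6.5.3.1): ("last dose date of avelumab – first dose date of avelumab + 14)/7".
- The end of the Arm A on-treatment period (SAP 5.2.7): "minimum (30 days + last dose of study treatment, start day of new anti-cancer drug therapy – 1 day").
- The immune-related AE definition (SAP Appendix 1), which accepts onset "anytime thereafter through 90 days after last dose of study treatment", whether or not new anti-cancer drug therapy has started.
- The tabulation of deaths within 30 days of last dose (SAP 6.6.2).
- The imputation of partial start dates for new anti-cancer therapy (SAP 5.3.3.4).

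**The concern.** A record with a known month in an earlier calendar year than the reference date has no outcome of its own. It fails outcome 1 because the month is known as well as the year. It fails outcome 2 because the years differ. It therefore takes the EOT or death date, which contradicts what the site recorded.

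This looks like an omission rather than a deliberate conservative choice, for two reasons. Outcomes 1 and 2 both keep the recorded parts of the date and take the latest day consistent with them; the catch-all breaks that principle only when the known month lies across a year end. And SAP 5.3.3.4, on start of new anti-cancer therapy, has the missing branch. Its condition "YYYY < Year of min [max(PD date + 1, last dose of study treatment + 1), end" (continuing to the therapy end date) leads to the last day of the recorded month.

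The error runs in one direction, toward a later date. It overstates avelumab exposure and can bring later AEs, laboratory abnormalities and deaths into windows where the record says they do not belong. If death is the reference date, the last dose is set to the day of death, so the death counts as within 30 days of last dose even when the recorded month rules that out.

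**Working it through.** There is no published figure to reproduce here; the check is to apply the rule as written.

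**Rules compared.** Let R be the earlier of EOT and death. The rule as written gives:

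- year only, year < year(R): 31 December of that year;
- year and month, year = year(R), month < month(R): last day of that month;
- all else: R.

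The corrected rule changes the second line to apply whenever (year, month) precedes (year(R), month(R)).

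**Derived quantities.** Exposure = (last dose − first dose + 14)/7 weeks. Uncapped on-treatment end = last dose + 30 days. Immune-related AE window end = last dose + 90 days.

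**Worked cases.** All dates are assumed for illustration, with first dose on 1 March 2018. Paired entries are as written / corrected.

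| Recorded last dose | R | Imputed last dose | Shift (days) | Exposure (weeks) | Uncapped on-treatment end |
|---|---|---|---|---|---|
| Dec 2018 | 10 Jan 2019 | 10 Jan 2019 / 31 Dec 2018 | 10 | 47.00 / 45.57 | 9 Feb 2019 / 30 Jan 2019 |
| Dec 2018 | 31 Jan 2019 | 31 Jan 2019 / 31 Dec 2018 | 31 | 50.00 / 45.57 | 2 Mar 2019 / 30 Jan 2019 |
| Nov 2018 | 20 Jan 2019 | 20 Jan 2019 / 30 Nov 2018 | 51 | 48.43 / 41.14 | 19 Feb 2019 / 30 Dec 2018 |
| Oct 2018 | 15 Jan 2019 | 15 Jan 2019 / 31 Oct 2018 | 76 | 47.71 / 36.86 | 14 Feb 2019 / 30 Nov 2018 |
| Nov 2018 | 20 Feb 2019 | 20 Feb 2019 / 30 Nov 2018 | 82 | 52.86 / 41.14 | 22 Mar 2019 / 30 Dec 2018 |
| 2018 (year only) | 10 Jan 2019 | 31 Dec 2018 / 31 Dec 2018 | 0 | 45.57 / 45.57 | 30 Jan 2019 / 30 Jan 2019 |

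The 82-day shift is 31 days of December + 31 of January + 20 of February. It adds 82/7 = 11.71 weeks of exposure (52.86 − 41.14, to rounding). The immune-related AE window end moves from 28 February to 21 May 2019.

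The first and last rows show that less information gives the better answer. With EOT on 10 January 2019, 2018 alone gives 31 December 2018; adding that the month was December gives 10 January 2019.

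The corrected date is the latest day the record allows, so each shift is the least by which the rule overshoots the true last dose. In the 82-day case the true overshoot is between 82 days (dose on 30 November) and 111 days (dose on 1 November).

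**How general the contradiction is.** The rule was run over every reference date from 1 January 2017 to 31 December 2019 (3 × 365 = 1,095 dates), with every known year or year and month from 2016 onward and not later than the reference.

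| Known parts | Combinations | Imputed date contradicts the record |
|---|---|---|
| Month and year, earlier year | 26,280 | 26,280 |
| Month and year, same year | 7,146 | 0 |
| Year only | 3,285 | 0 |

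The first count is 365 × (12 + 24 + 36). These are date combinations, not patients. They show that the fault is complete within the missing branch and absent elsewhere; they say nothing about how often it occurs.

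**The case against.** The strongest objection is that the rule will hardly ever be triggered. Avelumab is given at the site by study staff, infusion details go into source documents and the CRF, and the analysis uses cleaned data. The fault needs a last-dose record that lacks its day, keeps its month, and falls in a calendar year before EOT or death. That stands: the number of patients is likely very small.

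The 82-day example is also toward the long end. Protocol Table 3 allows a toxicity hold of up to 12 weeks (84 days) from last administration, so within that limit only a dose on 28 to 30 November fits an EOT on 20 February. Shorter gaps across a year end give smaller shifts, as the table shows.

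Several consequences have limits, and these stand too:

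- The on-treatment period stops the day before new anti-cancer drug therapy, so the shift in its end is a maximum. The 90-day immune-related AE window has no such cap.
- The imputed last dose affects a new-therapy start date only if that date is itself missing or partial. Even then it enters through a maximum with PD date + 1, capped by the therapy's end date, so any effect on PFS censoring would be rare.
- Dose intensity and relative dose intensity are not directly affected, because their denominator runs from the start of the last cycle.
- AEs are reported as numbers and percentages of patients, so a longer window can only add Arm A events and cannot hide toxicity.
- OS event times do not use this date, and date of last contact uses complete dates only.

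These points bound the effect. None supplies the missing branch, and nothing elsewhere in the SAP overrides 5.3.2.4 for this pattern.

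**Conclusion.** The concern holds. As written, SAP 5.3.2.4 gives a last dose that contradicts the recorded month in every case where that month lies in a calendar year before the earlier of EOT and death. In the illustrative cases the minimum overshoot runs from 10 to 82 days. The direction is always toward longer exposure and later windows, and the effect falls in practice on Arm A, because Arm B's end date is read from the disposition page.

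This is a minor point. It rests on partial last-dose dates occurring at all; the documents give no count and few are expected. No effect on the OS conclusion is claimed. It deserves correction because the rule is explicit and wrong, the intended behaviour is plain from its other branches and from 5.3.3.4, and nothing is lost by changing it.

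**What to change.** In SAP 5.3.2.4, replace the second condition so that, when year and month are both available, the last day of that month is imputed if the year is earlier than the year of the earlier of EOT and death, or if the years are equal and the month is earlier. Leave the other two outcomes unchanged. This removes every contradiction found above and brings the section into line with SAP 5.3.3.4.

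The cost is one condition in the SAP and one in the derivation program. For outputs already produced, list Arm A patients with a partial last-dose date in a calendar year before EOT or death. If there are none, record that. If there are some, rerun the affected exposure, on-treatment safety, immune-related AE and 30-day death summaries, and check those patients for any partial new-therapy start date.
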